Smartphone Software Applications

PACO: The Personal Analytics Companion (PACO Developers, 2018) is a mobile application software package for designing ecological momentary studies. It allows for fixed, user-editable, and stratified random prompting on personal iOS and Android phones. *Quip* (Taylor & Gibbs, 2018) is a mobile application for creating documents, task lists, and embedded spreadsheets that can be edited in real time by multiple users across multiple devices.

Procedure

All data was collected prior to the COVID-19 pandemic. Eligible participants were randomly assigned to either the SkillJoy treatment condition or the active self-monitoring (ASM) control condition. The interventions and organization of prompt times were informed by several rounds of pilot testing. After arriving at the laboratory, all participants were provided informed consent. They then completed baseline questionnaires using PsychData on a laboratory computer as well as a computerized task (for another study). They were then given a description and rationale for their assigned treatment conditions regarding how it would reduce their GAD symptoms and increase positive emotions (see supplementary materials). Subsequently, participants downloaded and started study apps. Each participant also received a Quip document

with their condition's rationale and instructions on how to complete each part of the intervention, an organized scheduling spreadsheet, and a note-taking space. They were trained on how to use their assigned app, assisted with a PowerPoint presentation to which participants had access throughout the study. At the end of the training session both groups were given information on following steps of the study, were reminded of the compliance check phone call on their fifth day of EMI use, and post-trial study tasks, and were given opportunities to ask questions.

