Statistical Analysis Plan

SkillJoy Randomized Controlled Trial

[name].^{1,2}

[name].²

Department of Psychology

Skidmore College¹

Pennsylvania State University²

May 5th, 2019

Planned Statistical Analyses

Power analysis with RMASS II suggested a need for 70 total participants for a two-level longitudinal linear mixed effects model of adequate power (0.80). To account for missing data, we used multiple imputation with 100 iterations of the Markov Chain Monte Carlo (MCMC) method, creating 10 imputed datasets. All results reflect analyses pooled across the imputed datasets. We then used longitudinal multilevel modeling for all outcome measure efficacy analyses. Regarding treatment outcome, longitudinal linear mixed models compared trends of change across time on all symptom, positive affect, and regulation strategy outcome measures between intervention conditions. These models all included the intercept, linear time trend, condition, and interaction between time trend and condition as fixed effects and the intercept as a random effect. Separate models were run to examine the change from baseline/pre-trial to eighth day post-trial (pre- to post-trial; the intervention phase) and from pre-trial to the 30th day follow-up (pre- to follow-up). We also examined the maintenance of treatment gains by comparing trajectories of change from eighth day post-trial measures to the 30th day follow-up. Simple slopes analyses were conducted for each outcome and learning variable within each condition.

Between-condition differences in baseline measures, degrees of missingness, and compliance rates were examined with independent samples t-tests. Reliable change index analyses used the formula of Jacobson and Truax (1991). Cohen's d was calculated in the traditional manner for t-tests, Cohen's $d = (M_2 - M_1) / SD_{pooled}$ where $SD_{pooled} = \sqrt{((SD_1^2 + SD_2^2) / 2)}$ (Cohen, 1988). In longitudinal linear mixed models and simple slopes analyses, Cohen's d was calculated with an alternative formula fit for multilevel models, $d = 2t / (\sqrt{df})$, as

recommended by Rosenthal (1994). Note that pre- to follow-up analyses are underpowered with the subset of our sample that completed follow-up measures ($n = 66$).

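### The two-group formula d = 2t/√df is also used for within-arm slopes, so within-arm and between-arm effect sizes are on different scales (a factor of 1.41 with 1:1 arms and a shared df)

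*SAP*

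**What the plan says.** All of this is in the SAP, Planned Statistical Analyses. Each efficacy model has an intercept, a time trend and condition, plus the "interaction between time trend and condition as fixed effects and the intercept as a random effect". The models cover two occasions at a time: "Separate models were run to examine the change from baseline/pre-trial to eighth day post-trial", with a further model from pre-trial to day 30 and a comparison from day 8 to day 30. Within-arm effects are reported too: "Simple slopes analyses were conducted for each outcome and learning variable within each condition".

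Two effect-size rules follow. For group comparisons by t-test, "Cohen's d was calculated in the traditional manner for t-tests", with a pooled SD written out. For everything else, "In longitudinal linear mixed models and simple slopes analyses, Cohen's d was calculated with an alternative formula fit for multilevel models", namely d = 2t/√df. No standardizing SD is named for this second d, and no rule says how df is obtained. Missing data are handled with 10 imputed datasets: "All results reflect analyses pooled across the imputed datasets".

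**The concern.** The time-by-condition interaction compares two independent groups. A simple slope describes change in one group. A t statistic from each needs a different multiplier to become a standardized effect, yet the SAP gives both the same one.

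Readers will set the SkillJoy within-arm d beside the between-arm d, or set either beside conventional benchmarks. If SkillJoy changes and the control does not, the two true effects are equal, but the rule reports the uncontrolled one as larger. The reliable change index concerns individuals and the pooled-SD d is tied to t-tests, so the SAP offers no other standardized efficacy measure to correct that impression. Without a stated df, a reader cannot undo the conversion.

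**Working it through.** **Inputs.** The formula, the two-occasion random-intercept model, the within-condition slopes and the 10 imputations come from the SAP, as do the planned total of 70 and the 66 follow-up completers. The Protocol (Procedure) says only that "Eligible participants were randomly assigned to either the SkillJoy treatment condition or the active self-monitoring (ASM) control condition", so 1:1 (35 per arm) is an assumption. The df is not stated, so several values are tried.

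**The plan's own figure.** The SAP prints no d values to reproduce. Its one planning figure, "Power analysis with RMASS II suggested a need for 70 total participants", cannot be rebuilt because alpha, effect size and correlation are missing. At an assumed two-sided alpha of 0.05, 35 per arm and power 0.80 imply a standardized effect of 0.67. Nothing below depends on this.

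**Algebra.** Let D be the raw change, S the SD of individual change and n the number per arm. Suppose the control does not change, so the within-arm and between-arm effects are both D/S.

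- Within-arm slope: t = (D/S)·√n, so 2t/√df = (D/S) × 2√(n/df). This is right only if df ≈ 4n.
- Interaction: t = (D/S)·√(n/2), so 2t/√df = (D/S) × 2√(n/(2df)). This is right only if df ≈ 2n.
- Ratio at any shared df: √2 = 1.41.

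| df (n = 35) | Possible origin | Slope factor | Interaction factor | Ratio |
|---|---|---|---|---|
| 34 | one arm fitted alone, n − 1 | 2.03 | – | 2.0 against the interaction at df 68 |
| 68 | N − 2 | 1.43 | 1.01 | 1.41 |
| 136 | observations, 2N − 4 | 1.01 | 0.72 | 1.41 |
| 900 | classical pooled df, see below | 0.39 | 0.28 | 1.41 |

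For example, at df 68 the slope factor is 2√(35/68) = 1.43 and the interaction factor is 2√(17.5/68) = 1.01.

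Unequal arms give a ratio of √(1 + n1/n2), where n1 is the arm whose slope is reported. For a 40:30 split that is 1.53 for the larger arm and 1.32 for the smaller; it always exceeds 1. With 33 per arm at follow-up (assumed, and only if completers are analysed), the slope factor is 1.44 at df 64 and 2.03 at df 32.

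**Model check.** The SAP's random-intercept model was fitted to 30 simulated trials of 35 per arm. The interaction standard error was 1.4142 times the slope standard error in every fit.

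**Undeclared scale.** At df 68 the interaction d is in units of the SD of change. Relative to a d in raw-score SD units (equal variances), it is 1.01/√(2(1 − ρ)): 0.86, 1.01 and 1.31 times as large at pre-post correlations ρ of 0.3, 0.5 and 0.7. These correlations are assumed.

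**Pooled df.** Take an illustrative t = 2.84 and an assumed fraction of variance due to missingness λ = 0.10. Classical pooled df is (10 − 1)/0.10² = 900; the small-sample version, with complete-data df 68, is 55.8. Then d = 2 × 2.84/√df is 0.69 at df 68, 0.76 at df 55.8 and 0.19 at df 900: one t, three effect sizes.

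**Simulation.** With 20,000 trials per setting, SkillJoy change 0.5 SD and control change 0, both true raw-SD effects are 0.50.

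| Correlation | df | Slope d | Interaction d |
|---|---|---|---|
| 0.3 | 68 | 0.61 | 0.43 |
| 0.5 | 68 | 0.73 | 0.51 |
| 0.5 | 136 | 0.51 | 0.36 |
| 0.5 | 34 (arm fitted alone) | 1.04 | – |
| 0.7 | 68 | 0.94 | 0.66 |

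Dividing each estimated change by the pre-trial SD instead returned 0.50 to 0.51 for both effects at all three correlations.

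**The case against.** The strongest reply is that the documents show inconsistent scaling, not inflated within-arm values. At df 136 the slope d is about right and the interaction d is the one that is off; at df 900 both are too small. This stands, and it is why the error is stated as relative to the between-arm d.

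Second, neither 1:1 allocation nor a shared df is in the documents, and pooling can give each coefficient its own df. That is fair for the exact figure of 1.41. It does not rescue the rule: unequal arms still give a ratio above 1, and coefficient-specific df would make the scale vary further.

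Third, the control is active and was presented to participants as helpful, so it may improve too. Part of any gap between within-arm and between-arm d would then be real. The scaling error would still multiply the within-arm value on top of that.

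Fourth, with df = N − 2 the interaction d is a legitimate effect size. This is correct, but the SAP says neither that this df is used nor that the unit is the SD of change.

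Fifth, a pre-trial SD is itself a choice. Everyone was selected on two GAD screens, which may narrow the baseline spread. The Protocol's PSWQ alphas (.78 pre, .87 post) would imply a post-trial SD √(.22/.13) = 1.30 times the pre-trial SD if error variance were constant. The choice should therefore be declared. In a check with the post-trial SD at 1.3 times the pre-trial SD, the pre-trial-SD measure still returned about 0.50 for both effects.

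**Conclusion.** The concern holds. Followed as written, the SAP puts within-arm and between-arm effect sizes on different scales, and no single df corrects both. The mismatch is exactly √2 = 1.41 with 1:1 arms and a shared df, 1.32 or 1.53 with a 40:30 split, and 2.0 if arms are fitted separately with half the df. The absolute size of either d cannot be settled from the documents, because neither the df rule nor the standardizing SD is given. The algebra is certain; the allocation ratio, df values, correlations and λ are assumptions. Only the reported effect sizes are affected, so this should be fixed but does not threaten the hypothesis tests.

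**What to change.** Replace the sentence giving d = 2t/√df with wording such as:

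> For each mixed model, d is the pooled estimate of the between-arm difference in change divided by SD_pooled (as defined above for t-tests) of that outcome at pre-trial. Its 95% CI is the pooled CI divided by the same SD, treated as fixed. For each simple slope, the standardized change is the pooled within-arm change divided by the same pre-trial SD. The same SD is used for the pre-post, pre-follow-up and post-follow-up models.

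Add one sentence stating how df is obtained for pooled t values. Both effects are then on one named scale, and neither depends on df.

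The cost is one or two sentences and a recomputation from estimates the models already produce; no new data are needed. Within-arm values may become less favourable, and between-arm values may move either way. The SAP already reports the number of follow-up completers, so the redefinition should be labelled as made after data collection.

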Study Protocol
SkillJoy Randomized Controlled Trial
[name].^{1,2}
[name].²
Department of Psychology
Skidmore College¹
Pennsylvania State University²
April 30th, 2018

Method

Participants

Participants were identified through the Pennsylvania State University subject pool. All those invited to participate via email met DSM-5 criteria for GAD on the *Generalized Anxiety Disorder Questionnaire-IV* (GAD-Q-IV; Newman et al., 2002). Those who accepted the invitation were then screened on the phone for GAD a second time by clinical interview (the GAD section of the Mini-International Neuropsychiatric Interview (MINI); Sheehan et al., 2015). They were required to meet full criteria for GAD on both the GAD-Q-IV and the MINI to participate. All participants were 18 years of age or older, spoke English, and were able to consent.

Measures

Primary outcome measures

The Penn State Worry Questionnaire (PSWQ; Meyer, Miller, Metzger, & Borkovec, 1990) is a 16-item self-report scale of the severity and frequency of worry. It has strong internal consistency .91, retest reliability ($r = 0.92$), convergent and discriminant validity, and sensitivity to change from psychotherapy (Brown, Antony, & Barlow, 1992; Meyer et al., 1990). In our sample, internal consistency was $\alpha = .78$ at pre-trial, .87 at post-trial, and .89 at follow-up.

The Positive and Negative Affect Schedule, Expanded Form: Joviality Scale (PANAS-X Joviality; Watson & Clark, 1994) is an 8-item measure of positive emotions. This joy sub-factor had an average factor loading of 0.73 (Egloff, Schmukle, Burns, Kohlmann, & Hock, 2003; Watson & Clark, 1994). It had strong internal consistency (median $\alpha = .93$) across eight studies of various time intervals (e.g., momentary, daily, past few days, past week, or past month; $\alpha = .88$ to $.94$), as well as convergent and discriminant validity (Watson & Clark, 1994). In our

sample, internal consistency was good (pre: $\alpha = .90$; post: $.88$; follow-up: $.92$).

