The Savoring the Moment Subscale of the Savoring Beliefs Inventory (SBI; Bryant, 2003). The SBI is a 14-item survey that measures beliefs about one's ability to savor. The savoring the moment subscale measures savoring of present-moment emotional experience. Confirmatory factor analysis showed all subscales had good fit (Bryant, 2003), had good-retest reliability ($r = .88$), and internal consistency reliability ($\alpha = .78$ for total scale), convergent and divergent validity. In our sample, internal consistency was good (pre: $\alpha = .80$; post: $.86$; follow-up: $.84$).

Secondary Outcome Measures

Responses to Positive Affect Scale (RPAS; Feldman, Joormann, & Johnson, 2008) was used to measure kill-joy thinking (a.k.a. "dampening"). Participants rated eight dampening items on a 5-point scale. The RPAS showed good model fit (RMSEA = 0.043; CFI = 0.94; RMSR = 0.049), internal consistency ($\alpha = 0.76 - 0.83$), convergent and discriminant validity (Feldman et al., 2008; Nelis, Holmes, & Raes, 2015). In our sample, internal consistency was good (pre: $\alpha = .86$; post: $.88$; follow-up: $.88$).

The Prioritizing Positivity Scale (PPS; Catalino et al., 2014) measured the degree to which participants prioritized seeking positive experiences on six items with which participants either agree or disagree on a nine-point scale. It had good model fit (CFI = .99; RMSEA = .04), internal consistency reliability ($\alpha = .81$), and good construct validity (Catalino et al., 2014). In our sample, internal consistency was good (pre: $\alpha = .83$; post: $.88$; follow-up: $.91$).

The Life Orientation Test – Revised (LOT-R; Scheier, Carver, & Bridges, 1994) measures optimism. It has 10 items rated on a four-point scale. It showed good model fit (CFI = .99, TLI = .99, RMSEA = .04), convergent, and discriminant validity (Glaesmer et al., 2012; Herzberg,

Glaesmer, & Hoyer, 2006). Internal consistency was acceptable in our sample (pre: $\alpha = .78$; post: $.82$; follow-up: $.82$).

The Beck Depression Inventory II (BDI-II; Beck, Steer, & Brown, 1996) is a widely used, 21-item self-report survey that measures the presence and severity of depressive symptoms. It has repeatedly demonstrated high internal consistency, such as $\alpha = 0.93$ (Beck et al., 1996). Convergent and discriminant validity have been demonstrated as well (Beck et al., 1996). In our sample, internal consistency was good (pre: $\alpha = .88$; post: $.93$; follow-up: $.95$).

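### The efficacy Cohen's d (2t/√df) is not in score-SD units: it varies with the pre-post correlation and an unstated df rule, so its values are not comparable across outcomes or windows

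*SAP*

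**What the plan says.** All of this is in the SAP, Planned Statistical Analyses. Each efficacy model has the intercept, time, condition and the "interaction between time trend and condition as fixed effects and the intercept as a random effect". The windows are analysed apart: "Separate models were run to examine the change from baseline/pre-trial to eighth day post-trial", with another model from pre-trial to day 30 and a maintenance comparison from day 8 to day 30. Results are pooled over 10 imputed datasets.

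Two effect sizes carry the name Cohen's d. For t-tests, "Cohen's d was calculated in the traditional manner for t-tests": a mean difference over the pooled SD of the scores. For the mixed models and simple slopes, it "was calculated with an alternative formula fit for multilevel models", d = 2t/√df. The SAP does not say what SD the second d is measured in, which df is used, or what the pre-post correlation is. This point concerns the between-arm (interaction) d only, not the simple slopes.

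**The concern.** Applied to a t from two independent groups measured once, 2t/√df returns a difference in SDs of the score. Applied to a condition-by-time t it does not, because the error term of that t is the variability of change within persons. A stable scale has a small SD of change and so a large d; an unstable scale has the reverse. The divisor then differs by outcome and by window, and nothing tells the reader so.

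The d values are how the trial expresses the size of benefit. A reader will naturally set them against the usual benchmarks, and will set one primary outcome against another, or day 8 against day 30. Those comparisons would mix the treatment effect with the stability of the scale and with the choice of df.

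**Working it through.** **Inputs.** From the SAP: the formula, the model, the windows, N = 70 from the power analysis, n = 66 at follow-up, 10 imputations. From the protocol, Primary outcome measures: sample alphas pre and post of .78 and .87 (PSWQ), .90 and .88 (Joviality), .80 and .86 (savoring subscale); published retest correlations of .92 (PSWQ) and .88 (SBI). Assumed: 35 per arm, two waves per model, and a range for r.

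**The plan's own figure.** The SAP gives no planned d. N = 70 cannot be reproduced, because effect size, alpha and correlation are not stated. Back-solving for 80% power at two-sided .05 gives (1.960 + 0.842) × √(2/35) = 0.67 SDs of the tested contrast. That is 0.67 score SDs at r = .5 but 0.42 at r = .8, so the target is not fixed in score units either.

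**Step 1: what 2t/√df measures.** With two complete waves, as in each imputed dataset, the interaction t equals the change-score t. Fitting the SAP's model to simulated trials gave 2.3157 against 2.3157, and 1.5894 against 1.5894. Let D be the between-arm difference in change. Then t = D/(SD_change × √(4/N)), and with df = N−2:

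2t/√df = (D/SD_change) × √(N/(N−2)).

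The last factor is √(70/68) = 1.015.

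**Step 2: link to score SDs.** With equal SDs at both waves, SD_change = SD × √(2(1−r)), so the ratio to the score-SD effect is 1/√(2(1−r)). For a true difference of 0.50 score SD, N = 70:

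| r | ratio | d with df = 68 | d with df = 136 |
|---|---|---|---|
| .3 | 0.85 | 0.43 | 0.30 |
| .5 | 1.00 | 0.51 | 0.36 |
| .7 | 1.29 | 0.66 | 0.46 |
| .8 | 1.58 | 0.80 | 0.57 |

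**Step 3: how large r can be.** Taking alpha as reliability, the observed pre-post r is capped near √(.78 × .87) = .82 for the PSWQ and √(.80 × .86) = .83 for savoring. The ratio is then at most about 1/√(2 × .17) = 1.7. Joviality's cap is higher: √(.90 × .88) = .89, a ratio of 1/√(2 × .11) = 2.13.

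**Step 4: the df rule.** With observation-level df (2N−4 = 136), d shrinks by about √2 and the crossover moves from r = .5 to about .75. With Rubin's large-sample df and 10 imputations, 10% missing information gives 9/.10² = 900. At r = .7 the pooled t is about 2.70 × √.9 = 2.56, so d = 2 × 2.56/√900 = 0.17 for the same 0.50. The Barnard-Rubin df of 55.8 gives 2 × 2.56/√55.8 = 0.69.

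**Step 5: across windows.** With D unchanged and one df rule, day-30 d over day-8 d is √((1−r8)/(1−r30)). With r8 = .8 and r30 = .6 this is √(.2/.4) = 0.71, a printed fall of 29% (0.80 to 0.57). With .7 and .5 it is 0.77, a fall of 23%. If r rose, d would grow. Dropping from 70 to 66 participants does not cause this: simulated d at r = .7 was 0.661 and 0.666.

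**Step 6: the alternative.** Dividing D by the pooled baseline SD gave a mean of 0.50 to 0.51 in simulation at every r from .4 to .8.

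**The case against.** The strongest reply is that the direction and size of any error are not established. That stands. A reader might infer that the formula overstates the benefit, by 2.50 for the PSWQ and 2.04 for the SBI if the retest values are put into step 2. The documents do not support this. Those correlations come from other samples, this sample's alphas imply a lower cap, and r in the trial is not reported. Below r = .5, or with a larger df, the formula understates. A reader might also infer a false fade by day 30. That needs a lower r over the longer window, which is plausible but undocumented; under Rubin's df, more missing data at day 30 would push d upward.

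Equal SDs are also an assumption. If error variance is constant, the PSWQ alphas imply a post-to-baseline SD ratio of √(.22/.13) = 1.30. Measured against the baseline SD, the crossover then moves to r = .65 and the ratio at r = .7 is 1/√(1 + 1.69 − 2 × .7 × 1.30) = 1.07.

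It can further be said that both formulas are printed, that the t-test d is meant for baseline, missingness and compliance differences, that maintenance has its own analysis, and that the standardiser is a reporting choice. All true. But printing a formula does not disclose its unit, and an effect size that depends on an unstated df cannot be interpreted.

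**Conclusion.** The point holds as a matter of units and comparability. With two waves and df near N−2, the efficacy d is in SDs of change. It differs from the score-SD effect by a factor of 0.85 to 1.58 for r from .3 to .8, and by at most about 1.7 for the PSWQ and savoring at their alpha-based caps. The unstated df rule can move it at least as much: 0.17 or 0.69 from the same data in the example. An apparent fade or growth between day 8 and day 30 with an unchanged difference is possible, not shown.

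This rests on two-wave models, equal SDs for the quoted factors, and alpha taken as reliability for the caps. If the pre-to-follow-up model used all three waves, d would be on yet another scale: 0.38 (days coded 0, 8, 30; df 138) against 0.66 for pre-to-post, with a constant 0.50 difference and r = .7. Tests and p values are unaffected. The change is worth making because the reported size of benefit is affected.

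**What to change.** Replace the sentence on d for the between-arm effects. Compute each d as the pooled model-estimated condition difference in change over the whole window (not per unit of time), divided by that scale's baseline SD pooled over both arms. Use the same denominator for pre-to-post, pre-to-follow-up and post-to-follow-up. Give a 95% CI by dividing the model's confidence limits by that SD. This removes the dependence on both r and df. Leave the models, t values and p values as they are.

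If 2t/√df is kept as well, label it as SDs of change and state the df rule and r for each outcome and window.

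The cost is a short SAP edit and a recalculation from existing output. The printed d values will change and may be smaller. Selecting participants on GAD criteria may restrict the baseline SD, which would itself enlarge d, so the baseline SDs should be reported with a note to that effect.
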